6.7.6. Physical Examination

Abnormalities identified from physical examination are recorded in the eCRF as Medical History or AEs as appropriate and will be listed and summarized as such [See Sections 6.4.3 (Medical History) and 6.7.3 (Adverse Events)].

For each physical examination body system, the number and percentage of patients with abnormalities at baseline and at each assessed timepoint will be summarized by treatment group and overall for the Safety Analysis Set.

Physical examination findings (normal / abnormal) and details of abnormalities will be listed for each patient at each assessed timepoint.

6.7.7. Other Safety Variables

6.7.7.1. Pain Assessment for Phase I if evaluable

Pain assessment data analyses are detailed below. They will be performed if data are evaluable.

In accordance with the baseline value definition in Section 5.1.2, the absolute and percentage change from baseline will be derived as follows:

Absolute change = (post-baseline value – baseline value)

Percentage change from baseline = [(post-baseline value – baseline value) / baseline value] \times 100

⇒ FLACC Scale

Number and percentages of patients by treatment group and overall in patients from the Safety Analysis Set will be provided for the following categories:

- Face (0 / 1 / 2)
- Legs (0 / 1 / 2)
- Activity (0 / 1 / 2)
- Cry (0 / 1 / 2)
- Consolability (0 / 1 / 2)

In addition, Assessment of Behavioural Score will be derived by summing all individual scores of the FLACC scale (Face + Legs + Activity + Cry + Consolability) and will result in a total score between 0 and 10.

In addition, from this score, the following categories will be derived:

- 0 =Relaxed and comfortable
- 1-3 = Mild discomfort
- 4-6 = Moderate pain

7-10 = Severe discomfort/pain

Descriptive statistics of this score will be provided in patients from the Safety Analysis Set:

- Observed values and absolute change from baseline at each assessed timepoint using default summary statistics for continuous variables
- A categorical summary will be provided using counts and percentages for baseline and post-baseline values
- ⇒ Numeric Pain Rating Scale

Descriptive statistics of Numeric Pain Rating Scale value will be performed in patients from the Safety Analysis Set:

- Observed values and absolute change from baseline at each assessed timepoint using default summary statistics for continuous variables.
- ⇒ Faces Pain Rating Scale

A categorical summary of Face Pain Rating Scale will be provided using counts and percentages for baseline and post-baseline values in patients from the Safety Analysis Set.

The categories are the followings:

- 0 = No Hurt
- 2 = Hurts Little Bit
- 4 = Hurts Little More
- 6 = Hurts Even More
- 8 = Hurts Whole Lot
- 10 = Hurts Worst

6.7.7.2. Orthostatic Hypotension

All information related to orthostatic hypotension will be described in patients from the Safety Analysis Set:

- Signs of orthostatic hypotension
- SBP (mmHg)
- DBP (mmHg)
- Heart Rate

All data collected in the corresponding eCRF form will also be presented in a data listing.

6.7.7.3. Pregnancy Test

Listing of pregnancy test data will be provided at each visit in patients from the Safety Analysis Set.

6.7.8. Interim Analysis and Data Monitoring

6.7.8.1. Data Monitoring Committee (DMC) Analyses

A DMC is established to assure patient safety and will function independently of all other individuals associated with the conduct of the trial, including site investigators participating in the trial. The DMC will consist of a minimum of 2 physicians whose expertise covers relevant specialties and, where applicable, a statistician.

During the conduct of Phase I the DMC will evaluate available safety information and recommend trial continuation or termination. If continuation is recommended, the DMC will recommend to the sponsor whether the dose should be escalated, de-escalated, or held at the same level based on the CRM.

At the completion of Phase I, the DMC will review relevant data and provide a recommendation regarding the MTD and RP2D.

During the conduct of Part 2, DMC meetings will be held on a regular basis to review cumulative safety data and evaluate whether the trial should be modified, stopped, or continue unchanged. The Sponsor Safety Committee will evaluate the recommendations from the DMC after each DMC meeting. Any significant finding/recommendation from the DMC and endorsed by the Sponsor Safety Committee will be communicated to the regulatory authorities and Institutional Review Board (IRB)/Ethics Committee (EC) as appropriate, and to the sites.

Responsibilities, procedures, content of the DMC packages, and workflow of the DMC are specified in the DMC Charter and DMC shells.

6.7.8.2. Phase I Analysis

As described above, at the end of Phase I, all efficacy and safety analyses corresponding to phase I as well as PK analyses will be performed in order to let DMC members provide recommendation regarding the MTD and RP2D to be selected for Phase II.

6.8. Pharmacokinetic Assessments

A listing of PK blood sample collection times and serum concentrations will be presented for Hu3F8-BsAb separately for all patients for the Safety Analysis Set.

Pharmacokinetic concentrations will be summarized for the Pharmacokinetics Analysis Set for each timepoint by treatment group using protocol scheduled times and appropriate summary statistics.

See Section 5.2.4 for the handling of serum concentrations that are BLQ.

6.8.1. Pharmacokinetic Analysis

The following PK parameters will be determined where possible from the concentrations of Hu3F8-BsAb in Phase I Cycle 1, assuming single dose parameters ('split-dose' on Days 1 and 8) using noncompartmental methods in validated software program Phoenix WinNonlin (Certara, Version 8.1 or higher):

Parameter	Definition
AUC _{0-tlast}	area under the concentration-time curve from time 0 to the time of the last quantifiable concentration $(t_{last})^a$
AUC _{0-8d}	area under the concentration-time curve over the time interval 0 to 8 days postdose
AUC _{0-28d}	area under the concentration-time curve over the time interval 0 to 28 days postdose
$AUC_{0-\infty}$	area under the concentration-time curve from time 0 extrapolated to infinity ^c
%AUC _{extrap}	percentage of area under the concentration-time curve due to extrapolation from the last quantifiable concentration to infinity
C _{max}	maximum observed concentration over 0 to 28 days
t _{max}	time of the maximum observed concentration
t _{1/2}	apparent terminal elimination half-life over 0 to 28 days
MRT	Mean residence time
CL	total clearance
V_{ss}	volume of distribution at steady state
DAUC _{0-tlast}	AUC _{0-tlast} normalized by dose ^c
DAUC _{0-28d}	AUC _{0-28d} normalized by dose ^c
$DAUC_{0\text{-}\infty}$	$\mathrm{AUC}_{0\text{-}\infty}$ normalized by dose ^{b,c}
DC _{max}	C _{max} normalized by dose ^c

Table 8 PK Parameters

^a The AUC will be calculated using the linear trapezoidal rule for increasing concentrations and the logarithmic rule for decreasing concentrations (linear up/log down rule).

^b Based on the last observed quantifiable concentration after 2nd dose in cycle

^c Calculated by dividing the parameter by mcg/kg/cycle

Additional PK parameters may be determined where appropriate.

Pharmacokinetic analysis will be carried out where possible using actual dose administered (mcg/kg/cycle) and actual postdose blood sampling times after start of infusion. If an actual time is missing nominal time may be used.

The parameters C_{max} , and t_{max} will be obtained directly from the concentration-time profiles. If C_{max} occurs at more than 1 timepoint, t_{max} will be assigned to the first occurrence of C_{max} .

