9.1.2 Dose-Escalation Plan and Dose Limiting Toxicity (DLT)

9.1.2.1 Dose-Escalation Plan

This is a Phase I trial to determine the MTD of hu3F8-BsAb that leads to DLT in approximately 15% of patients. Hu3F8-BsAb is dosed based on body weight (BW) rather than body surface area (BSA). Unlike chemotherapy for which clearance ultimately depends upon cardiac output which is dependent upon BSA, antibody distribution and clearance depend on total blood volume which is determined not by BSA, but by BW. Dose escalation will start at dose level 1, 0.0045 mcg/kg/dose (0.009 mcg/kg/cycle). Dose-escalation will be performed in two stages. In the first stage, the trial will accrue 1 patient per dose until the first \geq Grade 2 toxicity (except for Grade 2 sinus bradycardia, sinus tachycardia, fever, nausea, vomiting, diarrhea, urticaria, headache, paresthesia, electrolyte disturbances, pain) is encountered. The subsequent dose allocation will follow the Continual Reassessment Method (CRM). CRM assumes a simple model for the probability of a DLT as a function of dose, and uses the occurrence of toxicities in the patients enrolled in the trial to sequentially determine which dose to administer to a new patient. Patients will be assigned at each dose one at a time. New subjects will be allocated a dose as suggested by the CRM algorithm based on the toxicities of previously accrued patients. If DLT data are not available for the previously accrued 1 or 2 patients, the CRM will proceed with the dose as calculated with available toxicities/data, however if there are 3 enrolled patients with incomplete /outstanding DLT data, accrual will be paused. DLT data from at most 2 patients can be pending but no more than 2 patients are allowed to have incomplete DLT data. To protect patient safety, a dose escalation of more than one dose level is not permitted. We will examine 12 dose levels. (Table 4) Our initial estimates of DLT probabilities are: 0.001, 0.005, 0.01, 0.025, 0.05, 0.075, 0.10, 0.15, 0.25, 0.35, 0.45, 0.50 for doses 1-12, respectively. Thus, our a priori belief is that dose level 8 is the MTD. We assume that the dose- toxicity follows a hyperbolic tangent model P(DLT=yes at dose d)=($(\tanh d+1)/2$)^a, where a is the unknown parameter that we need to estimate in order to determine which dose is the MTD.A value of a=1.0 indicate that our prior beliefs were correct; while a value of a less than (greater than) 1.0 indicates that the combinations are more (less) toxic than believed. To reflect the uncertainty in our prior probability estimates, we assume it follows an exponential distribution (prior distribution) with mean 1.0. Dose escalation will be guided by the model after the occurrence of the first DLT. At that time, the above initial estimates of DLT might be revisited before model initiation to reflect the current knowledge on the safety profile and dose levels based on the observed data. We will enroll 30 evaluable patients. All patients who are enrolled in the study and receive their assigned dose are considered evaluable for toxicity. Additional subjects will be enrolled to replace any subjects who are enrolled, but do not receive treatment. In the

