2.1.1.3. Dose-Escalation Plan

This is a Phase I trial to determine the MTD of hu3F8-BsAb that leads to DLT in approximately 15% of patients. Hu3F8-BsAb is dosed based on Body Weight (BW) rather than Body Surface Area (BSA). Unlike chemotherapy for which clearance ultimately depends upon cardiac output which is dependent upon BSA, antibody distribution and clearance depend on total blood volume which is determined not by BSA, but by BW. Dose escalation will start at dose level 1, 0.0045 mcg/kg/dose (0.009 mcg/kg/cycle). Dose-escalation will be performed in two stages.

In the first stage, the trial will accrue 1 patient per dose until the first \geq Grade 2 toxicity (except for Grade 2 sinus bradycardia, sinus tachycardia, fever, nausea, vomiting, diarrhea, urticaria, headache, paresthesia, electrolyte disturbances, pain) is encountered. The subsequent dose allocation will follow the CRM. CRM assumes a simple model for the probability of a DLT as a function of dose and uses the occurrence of toxicities in the patients enrolled in the trial to sequentially determine which dose to administer to a new patient. Patients will be assigned at each dose one at a time. New patients will be allocated a dose as suggested by the CRM algorithm based on the toxicities of previously accrued patients. If DLT data are not available for the previously accrued 1 or 2 patients, the CRM will proceed with the dose as calculated with available toxicities/data, however if there are 3 enrolled patients with incomplete /outstanding DLT data, accrual will be paused. DLT data from at most 2 patients can be pending but no more than 2 patients are allowed to have incomplete DLT data. To protect patient safety, a dose escalation of more than one dose level is not permitted.

12 dose levels will be examined (See Table 1). The initial estimates of DLT probabilities are: **0.001, 0.005, 0.01, 0.025, 0.05, 0.075, 0.10, 0.15, 0.25, 0.35, 0.45, 0.50** for doses 1-12, respectively. Thus, the a priori belief is that dose level 8 is the MTD. It is assumed that the dose-toxicity follows a hyperbolic tangent model P(DLT=yes at dose d)=($(\tanh d+1)/2$)^a, where a is the unknown parameter that will have to be estimated in order to determine which dose is the MTD and d is "an adjusted dose level". A value of a=1.0 indicate that our prior beliefs were correct; while a value of a less than (greater than) 1.0 indicates that the combinations are more (less) toxic than believed.

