4	Hu3F8-BsAb 2.6 mcg/kg/cycle	2.6 mcg/kg
5	Hu3F8-BsAb 4.8 mcg/kg/cycle	4.8 mcg/kg
6	Hu3F8-BsAb 9.3 mcg/kg/cycle	9.3 mcg/kg
7	Hu3F8-BsAb 21.3 mcg/kg/cycle	21.3 mcg/kg
8	Hu3F8-BsAb 41.3 mcg/kg/cycle	41.3 mcg/kg
9	Hu3F8-BsAb 81.3 mcg/kg/cycle	81.3 mcg/kg
10	Hu3F8-BsAb 161.3 mcg/kg/cycle	161.3 mcg/kg
11	Hu3F8-BsAb 301.3 mcg/kg/cycle	301.3 mcg/kg
12	Hu3F8-BsAb 501.3 mcg/kg/cycle	501.3 mcg/kg

Table 5 Treatment Labels for Phase I

If dose is changed after cycle 2 in phase I, tumor response will be evaluated based on the combination of the doses. Thus, some additional columns may be added.

Table 6 Treatment Labels for Phase II

Ordering	Full treatment group (a minima for	Short format labels (for use when
	listings)	space is limited) for tables
13	Hu3F8-BsAb RP2D Group 1	Hu3F8-BsAb RP2D NB
	(Neuroblastoma)	
14	Hu3F8-BsAb RP2D Group 2	Hu3F8-BsAb RP2D OS
	(Osteosarcoma)	
15	Hu3F8-BsAb RP2D Overall	Hu3F8-BsAb RP2D Overall

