6.7. Safety

6.7.1. Extent of Exposure

Duration of exposure will be defined in months as:

- If last dose is a priming dose, then:

Exposure (months) = ([date of last dose – date of first dose] + 7)/30.4375

- If last dose is a therapeutic dose, then:

Exposure (months) = ([date of last dose – date of first dose] + 21)/30.4375

Duration of exposure in days will be summarized for the Safety Analysis Set by treatment group and overall. Descriptive statistics will be presented for duration of exposure.

The duration of exposure will also be computed in weeks (dividing by 7 the above computations), and summarized by treatment group, in patients from the Safety Analysis Set for following variables:

- Duration as continuous (in weeks) using descriptive statistics
- Categorized by time intervals (<4 weeks, 4-<8 weeks, ...) for which frequency counts and percentages of patients will be provided.
- Descriptive statistics will also be summarized for the total number of cycles received per patient, the number of doses received at Day 1, the number of doses received at Day 8.

The total dose of treatment in mcg/kg taken over the trial duration will be calculated as the total sum of all infusions received during the trial.

The total dose of treatment in mcg/kg taken over the trial duration will be summarized alongside dosing changes for the Safety Analysis Set by treatment group and overall as:

• Descriptive statistics will be presented for total dose of treatment (sum of actual dose received).

A listing of overall treatment exposure data, including the first and last dates of treatment will be presented together with compliance for the Safety Analysis Set. Further, trial treatment infusion data will be listed for the Safety Analysis Set.

Treatment interruptions due to Covid-19 will also be described if applicable.

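### Dose-normalised Cmax is divided by the two-infusion cycle dose, so it is not comparable between levels with different Day 1/Day 8 splits or between patients given one and two infusions

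*SAP*

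**What the plan says.** SAP 6.8.1 derives the cycle 1 parameters "assuming single dose parameters ('split-dose' on Days 1 and 8) using noncompartmental methods". Table 8 defines Cmax as the "maximum observed concentration over 0 to 28 days". The footnote attached to DCmax, and to the dose-normalised AUCs, is "Calculated by dividing the parameter by mcg/kg/cycle". The same section uses the dose actually administered where possible. Protocol 14.1.2.1 asks for dose-normalised AUC and Cmax but names no divisor.

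On the split between the two infusions:

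- Level 1 is printed as an equal split in both documents: "0.0045 mcg/kg/dose (0.009 mcg/kg/cycle" in Protocol 9.1.2.1, and the same figures in SAP 2.1.1.3.
- SAP 6.7.1 distinguishes two kinds of dose. The branch opening "If last dose is a priming dose" adds 7 days of exposure, so the priming dose is the Day 1 dose. The therapeutic dose adds 21 days, so it is the Day 8 dose.
- SAP 6.6.3.6.1 uses the logarithm of the therapeutic dose, not of the cycle dose, as a covariate.
- SAP 2.3.1 says that the amended dose levels are level 5 and higher.
- The Day 1 and Day 8 columns of Protocol Table 4 and SAP Table 1 are blank in the public text. Only the cycle totals are available (SAP Table 5).

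On use: SAP 6.8.2 plans summary tables of the PK parameters by treatment. SAP 6.7.8.2 has the PK analyses performed so that the DMC can recommend an MTD and RP2D.

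**The concern.** Dividing by the cycle dose is coherent for an AUC that spans both infusions, because both contribute to it in full. A peak is different. Two infusions a week apart do not add at the peak, except through the residue of the first. Calling the cycle a split single dose does not change that.

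If every level used the same split, the wrong divisor would only rescale DCmax. The SAP's own terms indicate that the split differs: equal at level 1, priming followed by therapeutic elsewhere. A table of DCmax by dose level would then rise across that boundary even with perfectly proportional PK, and a reader would naturally take the rise as more-than-proportional exposure.

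The same problem arises within a level. The PK Analysis Set (SAP 4.6) admits anyone with one dose and one valid concentration, and Protocol 9.1.4 foresees that dose 2 may not be given on Day 8. A patient with only the Day 1 infusion has a one-infusion peak over a one-infusion dose; a patient with both infusions does not.

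**Working it through.** The documents give no DCmax value or ratio to reproduce. The one printed split checks: 2 × 0.0045 = 0.009 mcg/kg/cycle.

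**Inputs**

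- Cycle totals from SAP Table 5: 2.6 (level 4), 4.8 (level 5), 9.3 (level 6), 21.3 (level 7), rising to 501.3 (level 12) mcg/kg.
- Inferred, not printed: a Day 1 dose P = 1.3 mcg/kg at levels 5 to 12. It is half of level 4's 2.6, and it leaves round remainders from level 6 up (8, 20, … 500), with 3.5 at level 5.
- Comparator: an equal split. This is printed for level 1 only.
- Assumed: the fraction r of the Day 1 peak still present at Day 8. The documents give no half-life. With one compartment, r = 2^(−7/half-life in days). I take r from 0 to 0.7, that is, half-lives from near 0 to about 14 days.

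**Formulas (linear PK, c = peak per unit of infused dose, T = Day 8 dose)**

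- Cmax = c(T + rP), so the SAP's DCmax = c(T + rP)/(P + T).
- Equal split: DCmax = c(1 + r)/2.
- False ratio against an equal split = 2(T + rP)/[(P + T)(1 + r)]. With no artefact this would be 1.

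Example, level 12 with r = 0.5: (500 + 0.65)/501.3 = 0.9987; divided by 0.75 this is 1.33. Level 5 with r = 0.5: (3.5 + 0.65)/4.8 = 0.865; divided by 0.75 this is 1.15.

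| r | Half-life (days) | Level 5 | Level 6 | Level 7 | Level 12 |
|---|---|---|---|---|---|
| 0 | near 0 | 1.458 | 1.720 | 1.878 | 1.995 |
| 0.1 | 2.1 | 1.375 | 1.589 | 1.718 | 1.814 |
| 0.2 | 3.0 | 1.306 | 1.480 | 1.585 | 1.663 |
| 0.3 | 4.0 | 1.247 | 1.388 | 1.473 | 1.536 |
| 0.5 | 7.0 | 1.153 | 1.240 | 1.293 | 1.332 |
| 0.7 | 13.6 | 1.081 | 1.127 | 1.155 | 1.176 |

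The ratio exceeds 1 at every inferred level 5 to 12 whenever r < 1.

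**Sensitivity to the inferred split (r = 0).** Moving P from 0.5 to 2.4 mcg/kg moves the level 5 ratio from 1.79 to 1.00, because 2.4 is an equal split there. Level 12 stays at 1.99 to 2.00.

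**Within levels 5 to 12 (r = 0).** The Day 8 share rises from 0.729 to 0.997, so DCmax rises 0.997/0.729 = 1.37-fold. From level 7 to level 12 it rises only 0.997/0.939 = 1.06-fold.

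**One versus two infusions at level 1 (no inferred split needed).** With the actual dose as divisor, Day 1 only gives c and both infusions give c(1 + r)/2. The ratio is 2/(1 + r): 2.00 at r = 0 and 1.33 at r = 0.5.

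**Check of candidate fixes**

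- Overall Cmax over the dose of the infusion just before it: c(1 + r) for an equal split and c(T + rP)/T otherwise. Relative to an equal split, levels 5 to 12 give 1.00 at r = 0, but 0.895 down to 0.834 at r = 0.2 and 0.790 down to 0.668 at r = 0.5. It over-corrects.
- Day 1 Cmax over Day 1 dose: c at every level and for any r, so the ratio is 1.00.
- Day 8 Cmax minus the Day 8 pre-dose value, over Day 8 dose: c(T + rP − rP)/T = c, apart from the small decay of the residue during the infusion.

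**The case against.** The strongest reply is that little rests on DCmax. The fallback rule for the RP2D (Protocol 4.1.1, 9.1.2.1 and 14.1.1; SAP 2.1.1.1 and 2.1.1.3) looks to serum levels, with no mention of dose normalisation. Neither document plans a dose-proportionality test. A reader might infer that the footnote could send the trial to the wrong RP2D; the documents do not support that. The DMC's PK material would also include unnormalised Cmax, AUCs and concentrations at each time point. The near-peak samples after each infusion are therefore already summarised separately, tmax shows which infusion produced the peak, and the SAP allows additional parameters. This stands, and it limits the consequence to interpretation.

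A second reply is that the size is unknown. A reader might quote a flat 1.3- to 2-fold artefact. That would require leaving out levels 5 and 6 and half-lives beyond 7 days. Under the inferred splits, a ratio of at least 1.3 at all of levels 5 to 12 needs r of about 0.21 or less, a half-life of about 3 days or less. This stands too.

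A third reply is that where a plateau would be read, among the highest levels, the artefact is small: about 6% from level 7 to level 12. That is right, but the boundary with the equal-split levels and the rise from level 5 remain.

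Last, the split single-dose approach is a stated choice, and SAP section 7 relies on it to drop the accumulation indices. It justifies the cycle-dose divisor for AUC. It does not make a one-infusion peak comparable across splits.

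**Conclusion.** The point holds as a defect of interpretability in a descriptive PK parameter. The mechanism and direction follow from the SAP's own definitions under linear PK with incomplete carry-over: DCmax is falsely higher where most of the dose is given on Day 8, and it also differs between patients given one and two infusions.

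The size is about 1.1- to 2-fold against an equal split (1.08 at level 5 with a half-life near 14 days; 1.995 at level 12 with no carry-over). This rests on three assumptions that the documents do not settle: a 1.3 mcg/kg Day 1 dose at levels 5 to 12, a one-compartment decline, and the half-life range. The sponsor, who has the unredacted dose table, can replace the first with fact.

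What is at stake is a misleading dose-proportionality reading in the summaries that support the DMC. The primary analysis is not affected, and no direct error in the RP2D rule is shown.

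**What to change.** In SAP Table 8, replace the per-cycle DCmax with two parameters:

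- Day 1 Cmax divided by the actual Day 1 dose.
- Day 8 Cmax minus the Day 8 pre-dose concentration, divided by the actual Day 8 dose.

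Restrict the mcg/kg/cycle footnote to the AUCs that cover both infusions. State how a Day 8 pre-dose value below the limit of quantification enters the subtraction (for instance as zero), because SAP 6.8.1.3 would otherwise treat it as missing.

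Do not simply divide the overall Cmax by the dose of the infusion that preceded it. At the highest levels that produces a false difference of about 1 + r in the opposite direction, against about 2/(1 + r) under the current rule. It is therefore worse than the current rule once (1 + r)² > 2, that is, r above 0.41 or a half-life above about 5.5 days.

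The cost is a revised table entry and footnote and one extra derived parameter. Protocol 9.1.4 (Table 5) already schedules the samples about 5 minutes after each infusion and the Day 8 pre-dose sample. No new samples and no change to dosing are involved.
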